2.1.2.5 Screening failure

Screening failures are patients who enrolled and failed screening criteria in a study. These patients are never randomized. Patients who are randomized, but never received study treatment in a randomized study, are not screening failures.

2.1.2.6 Study day

The study day *for safety assessments* (e.g. adverse event onset, laboratory abnormality occurrence, vital sign measurement, dose interruption etc.) will be calculated as the difference between the date of the event (onset date of an event, assessment date etc.) and the start of study treatment plus 1. The first day of study treatment is therefore study day 1. If an event starts after the start date of study treatment, the study day will be calculated as:

Study day=date of event – start date of study treatment+1

If an event date is before the treatment start date, the study day will be calculated using the below formula:

Study day= date of event – start date of study treatment

The study day *for efficacy assessments* will be calculated as:

Study day = The date of the assessment / event - randomization date + 1

In other words, all efficacy, including time-to-event variables (event-free survival, overall survival, time to disease progression), will be calculated from the date of randomization.

For any assessment or events, such as baseline disease characteristics or medical history (e.g., time since diagnosis of disease) collected prior to randomization date, the study day will be negative and will be calculated as:

Study Day = Event date - Randomization date.

The study day will be displayed in the data listings.

2.1.2.7 Month

A month will be calculated as (365.25 / 12) = 30.4375 days. If duration is to be reported in months, duration in days will be divided by 30.4375.

2.1.2.8 **Baseline**

Unless otherwise specified below, for *efficacy evaluations*, the baseline value is defined as the last available measurement before or on the day of randomization (including results from unscheduled visits analyzed by the central laboratory). It is assumed that assessments scheduled for Visit 3 – the randomization visit – were done prior to randomization in order to be interpreted as *prior to or on the day of randomization* (e.g. physical examination, chest x-ray). If an assessment is done at both screening visits, Visit 1 and Visit 2, the value of Visit 2 is considered the baseline value.

Differing definitions for baseline values were specified for the following assessments or parameters:

• Serum creatinine, creatinine clearance, ALT/AST, serum ferritin, total and direct bilirubin: the baseline value is defined as the mean of the Visit 1 and Visit 2 values. If additional measurements analyzed by the central laboratory are available from

unscheduled visits in the screening period, they will be included in the average. Only the central lab values between -35 days and day 1 from randomization date will be considered to determine baseline.

• Transfusion history: data of platelet and PRBC transfusion records in the 6-month period prior to study start (randomization) will be used to establish baseline transfusion frequency and hematologic counts.

For *safety evaluations* (e.g., laboratory and vital signs etc.), the last available assessment before or on the date of start of study treatment is taken as the 'baseline' assessment.

If patients have no value as defined above, the baseline result will be missing.

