# 4 Study design

This is a prospective, randomized, double-blind, placebo-controlled, parallel group design study.

A screening period lasting up to 35 days with two screening visits (Visit 1 and Visit 2 - at least 14 days apart.) will be used to assess patient eligibility. Should the 35 day screening period be exceeded due to delays in scheduling exams as outlined in the protocol (such as ocular exams, audiometry testing, ECHO, etc.) this delay will not be considered a protocol deviation and all laboratory assessments outlined in Visit 1 must be repeated. In the event that it is more convenient for the site, confirmatory laboratory assessments may be collected by a local laboratory. Prior to a patient being randomized in the study (Visit 3), both the inclusion and exclusion criteria must be evaluated and documented in the source documents as being met and the results of all screening assessments must be available and reviewed by the investigator. At the randomization visit (Visit 3), patients will be randomized to 10 mg/kg/day of either deferasirox or matching placebo in a 2:1 manner in favor of deferasirox. As a control medication, placebo matching to each of the strength of the active compound will be utilized.

Randomization will be stratified using an interactive voice/web response system (IVRS/IWRS). The stratification will be defined by IPSS (low or int-1) as well as by geographical region (Asian versus non-Asian countries) since the Asian population have a longer survival (Matsuda 2005). Details on stratification will be outlined in the study manual provided by the IVRS vendor. Starting from Day 1, patients will receive either deferasirox 10 mg/kg/day or matching placebo for 2 weeks. At Week 2, the dose will be increased to 20 mg/kg/day deferasirox or matching placebo in all patients. This dose should be maintained through Week 14 unless there is a safety related issue (see Section 6.1.2.1). After 3 months of treatment, at the dose of 20mg/kg/day, dose may be adjusted by 5 to 10 mg/kg/day up to 40 mg/kg/day based on serum ferritin response.

Study treatment should be administered by the patient once per day. During the treatment period, patients will return every 4 weeks to the site for routine procedures and for follow-up to monitor safety, efficacy and compliance with therapy. Should a patient require dose adjustments at any point during the trial, the patient may be asked to return more frequently to monitor safety and efficacy.

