### 7.5.5.2 Biochemistry

Blood samples will be sent to the central laboratory as outlined in Table 7-1.

During the first month of treatment, serum creatinine will be measured weekly and preferably via local laboratory assessment. From Week 4 through-End of treatment, serum creatinine levels will be checked at every routine clinic visit. The central laboratory will calculate the creatinine clearance at every visit.

Serum ferritin test will also be performed at screening (Visit 1 and Visit 2) to assess the eligibility of the patient and should be drawn at least 14 days apart. The baseline serum ferritin value is defined as the average of the two measurements obtained during the screening period. Serum ferritin testing will also be performed at every visit starting at week 2 (Visit 4). Samples should be obtained in the absence of known inflammation or infection. If transfusion is scheduled, blood should be drawn for serum ferritin collection prior to transfusion or two weeks post-transfusion. Results will be provided to the sites within 24 hours after the central laboratory receives the sample.

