2.5.3.6 Increase in serum ferritin

For the analysis of time from randomization to the first occurrence of serum ferritin > 2 times the baseline value at two consecutive assessments (at least two weeks apart), patients who did not experience such an increase in serum ferritin will be censored at the last date when serum ferritin was available or at the date of randomization if no post baseline serum ferritin is available.

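### SAP 2.1.2.8 counts only central values from day -35 to day 1 as baseline, so a patient whose screening was validly extended, with repeat labs done locally, can have a one-value or missing ferritin baseline

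*SAP*

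**What the plan says.** Protocol section 4 plans "A screening period lasting up to 35 days with two screening visits (Visit 1 and Visit 2 - at least 14 days apart". If exam scheduling (ocular, audiometry, ECHO and the like) pushes screening past that length, "this delay will not be considered a protocol deviation and all laboratory assessments outlined in Visit 1 must be repeated". For site convenience, "confirmatory laboratory assessments may be collected by a local laboratory". The section sets no upper limit on the extension.

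For ferritin, protocol 7.5.5.2 states: "The baseline serum ferritin value is defined as the average of the two measurements obtained during the screening period". Protocol 5.1 uses the same two-visit mean for eligibility.

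SAP 2.1.2.8 starts from the same place for serum creatinine, creatinine clearance, ALT/AST, ferritin and bilirubin: "the baseline value is defined as the mean of the Visit 1 and Visit 2 values", with unscheduled central screening values added to the average. It then restricts the source and the dates: "Only the central lab values between -35 days and day 1 from randomization date will be considered to determine baseline". There is no fallback: "If patients have no value as defined above, the baseline result will be missing". The Baseline row of the window table in SAP 5.5.5 has the same limits, day -35 to day 1.

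For the ferritin-doubling endpoint, SAP 2.5.3.6 says that "patients who did not experience such an increase in serum ferritin will be censored at the last date when serum ferritin was available". A patient with no post-baseline ferritin is censored at randomization. A patient with no baseline ferritin is not mentioned.

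**The concern.** The two documents do not fit together for a patient the protocol treats as compliant. The protocol accepts a screening period longer than 35 days and a local repeat. The SAP then rejects both the older central values and the local repeat. Local values cannot fill the gap, because SAP 2.8.3 bars them from primary and secondary endpoint evaluation. Protocol 10.5.2.4 adds that, apart from weekly creatinine monitoring, only central results enter the database.

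Ferritin doubling is defined against baseline. If baseline is one value instead of two, the threshold moves away from the one the protocol defines. If baseline is missing, the criterion cannot be evaluated. Read literally, the censoring rule still credits that patient with event-free follow-up to the last ferritin.

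**Working it through.** **Inputs.** Visit 2 is at least 14 days after Visit 1 (protocol 4). A value counts only if it is central and -35 <= day <= 1 (SAP 2.1.2.8). Day is the sample date minus the randomization date. The repeat is taken as local and no other central value lies in the window.

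**Step 1: which scheduled values survive.** Visit 1 is lost when V1 <= -36. Visit 2 is certain to survive when V1 + 14 >= -35, that is V1 >= -49. Visit 2 can be lost only when V1 + 14 <= -36, that is V1 <= -50. Enumerating the dates gives the same boundary.

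| Visit 1 | Visit 2 | SAP baseline |
|---|---|---|
| day -35 or later | in window | two-visit mean, as in the protocol |
| days -36 to -49 | always day -35 or later | one value (Visit 2) |
| day -50 or earlier | day -35 or later | one value (Visit 2) |
| day -50 or earlier | day -36 or earlier | missing |

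A missing baseline therefore needs an overrun of at least 50 - 35 = 15 days, an early Visit 2, a local repeat and no other central value in the window.

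**Step 2: effect of a one-value baseline.** Illustration with assumed ferritin values of 1300 mcg/L at Visit 1 and 900 mcg/L at Visit 2:
- Protocol baseline: (1300 + 900)/2 = 1100, which is eligible (>1000). Doubling threshold: 2 x 1100 = 2200.
- SAP baseline with Visit 1 dropped: 900. Doubling threshold: 2 x 900 = 1800.

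The shift can go either way, depending on which visit was higher.

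**Step 3: effect of a missing baseline.** Let a fraction m of each arm have no baseline and stay at risk with no event possible. An event proportion p becomes (1 - m)p, and the difference between arms shrinks by the same factor. With an assumed p = 40%:
- m = 5%: 0.95 x 40% = 38%
- m = 20%: 0.80 x 40% = 32%

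For the hazard ratio, the hazard in an arm among everyone still at risk is λ(1 - m)S(t) / [m + (1 - m)S(t)]. At t = 0 the ratio of the two arms equals the true HR. It drifts towards 1 only as patients who can have an event leave the risk set. I solved the large-sample Cox score equation under assumed exponential times, 3 years of follow-up, 2:1 allocation and placebo event proportions of 20% to 60%:

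| m | true HR 0.50 becomes | true HR 0.70 becomes |
|---|---|---|
| 5% | 0.502 to 0.508 | 0.701 to 0.707 |
| 20% | 0.506 to 0.529 | 0.705 to 0.725 |

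**Step 4: number of patients.** The documents give no count of extended screenings or local repeats. For scale only, 5% to 20% of 210 patients is 0.05 x 210 = 10.5 to 0.20 x 210 = 42. If that were the share of extended screenings, the number with a missing baseline would be no larger, and smaller unless every such patient met all the conditions in Step 1.

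**The case against.** The best case for leaving the SAP alone is that the ordinary route works. The Visit 1 labs must be repeated once screening overruns, and Table 7-1 lists ferritin, ALT/AST and bilirubin at Visit 1. The central laboratory is the default (protocol 7.5.5), and the synopsis describes ferritin as a central assay. A central repeat inside the window gives a baseline, and the SAP already averages in unscheduled central values. The 35-day limit also mirrors the protocol's own view that older labs need repeating. All of this stands, and it narrows the problem to patients who used the local option. It does not remove the problem: that option is written into the protocol, the SAP has no rule for it, and even for a central repeat the SAP does not say whether it replaces Visit 1 or counts as unscheduled.

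A reader might infer four stronger things that the documents do not support.
- *That extended screening generally means no baseline.* For overruns of up to 14 days Visit 2 always survives.
- *That the liver component of event-free survival is compromised because it requires ALT or AST above twice baseline.* SAP 2.5.1 makes the adjudication committee's decision the one that counts, and neither document says the committee works from the SAP-derived baseline.
- *That the creatinine endpoints are lost.* Renal dysfunction is defined against ULN. The baseline-relative creatinine criterion is a safety summary, and the safety baseline is the last available assessment, with no day -35 limit in that rule. Table 7-1 also schedules creatinine at Visit 3.
- *That the treatment comparison is pulled materially towards no effect.* The overrun happens before randomization, so it should be balanced in expectation, and Step 3 shows that the hazard ratio then changes little.

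**Conclusion.** The mismatch is real but narrow. For compliant patients with an extended screening and a local repeat, SAP 2.1.2.8 replaces the protocol's two-visit mean with a single value or, under the conditions in Step 1, with nothing. The endpoint shown to be affected is ferritin doubling, a secondary endpoint in a study with no confirmatory tests. Its threshold changes for some patients, and others contribute follow-up in which an event cannot be recorded. The second effect lowers absolute event rates by the missing fraction. It has little effect on the hazard ratio, provided the missing fraction is similar in the two arms. The number of patients cannot be derived from the documents. The point merits correction because a stated rule gives a wrong result for patients who followed the protocol and the remedy is cheap, not because the main conclusions are at risk.

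**What to change.** 1. In SAP 2.1.2.8, for screenings extended under protocol section 4, define baseline as the mean of the central-laboratory Visit 1, Visit 2, repeat and unscheduled values from the qualifying screening episode up to randomization. State how a repeat is counted, as a replacement or as an additional value.
2. Align the Baseline row of the window table in SAP 5.5.5.
3. In SAP 2.5.3.6, take any patient who still has no central baseline out of the ferritin-doubling risk set, and report the number by arm. SAP 2.7.1.1 already does this for hematologic improvement when pre-treatment values cannot be determined. It is a small departure from the full analysis set, but it depends only on pre-randomization data.
4. Do not fill the gap with local values. That would contradict SAP 2.8.3, and protocol 10.5.2.4 suggests they may not be in the database.

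The cost is a few lines of SAP text and programming. Central Visit 1 and Visit 2 ferritin values should already exist, because eligibility used their mean. Some baseline values will be older than 35 days, with no stated upper limit on age, so they should be flagged. The change should be made before unblinding, so that the baseline rule is not chosen after the results are known.

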2.1.2.9 On-treatment assessment/event and observation periods

The overall observation period will be divided into three mutually exclusive segments:

- 1. *pre-treatment period*: before the first administration of study treatment
- 2. *on-treatment period*: from date of first administration of study treatment to 28 days after date of last actual administration of any study treatment (including start and stop date)
- 3. *post-treatment period*: starts on day 28+1 after last administration of study treatment.

Per study design, there will be two additional observation periods:

- 4. *study evaluation period:* starts on day 29 after last administration of study treatment until study evaluation completion period (visit frequency every three months)
- 5. **survival follow-up period:** starts after study evaluation completion visit until LPFV plus three years or death. If a patient declines to participate in the evaluation period, the survival follow-up period will start on day 29 after last administration of study treatment until LPFV plus three years or death (visit frequency is every 6 months).

2.2 Analysis sets

The following three analysis sets were defined for analyses in the study protocol.

2.2.1 Full Analysis Set

The Full Analysis Set (FAS) includes all patients to whom study treatment has been assigned by randomization. According to the intention to treat principle, patients will be analyzed according to the study treatment and strata they were assigned to during the randomization procedure (IVRS).

2.2.2 Per Protocol Analysis Set

The per protocol analysis set (PPS) is a subset of the FAS and comprises all randomized patients:

 Whose first administered study medication is in accordance with the randomized assignment, and

- Without protocol deviations regarding inclusion or exclusion criteria with respect to underlying disease, such as:
 - No low or intermediate-1 MDS according to IPSS score in the eCRF,
 - Serum ferritin ≤ 1000 μg/L at Screening,
 - More than 3 years since patient began receiving regular transfusions,
 - LVEF < 50%,
 - Diagnosis of liver cirrhosis

Also patients with the following protocol deviation will be excluded from the PPS:

- No bone marrow biopsy within 6 months of entering study
- Stratum assignment differs from MDS risk and / or country reported by investigator
- Patient randomized but received wrong study drug (first administered study medication)
- Prohibited concomitant medications:
 - Aluminium containing antacid therapies (aluminium hydroxide and magnesium hydroxide)
 - Use of bile sequestrants (e.g. cholestyramine, colesevelam, colestipol)
 - Use of any other chelation therapy (e.g. deferoxamine, deferiprone)
 - Any investigational drugs other than study medication.
 - Use of hormonal contraceptive (oral or injected)

Patients will also be excluded from per-protocol set according to VAP M3.

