#### Inclusion/exclusion criteria

#### 5.1 Inclusion criteria

- Male or female patients,  $\geq 18$  years of age
- Patient must weigh between 35–135 kg
- Patients with low or intermediate (int-1) risk MDS, as determined by IPSS score. This must be confirmed by a bone marrow examination within 6 months prior to study entry and must be hematologically stable
- Ferritin > 1000 mcg/L at screening
  - Serum ferritin will be measured at Screening Visit 1 and Screening Visit 2 (at least 14 days apart) and the mean value will be used for eligibility criteria.
- History of transfusion of 15 to 75 PRBC units
- Anticipated to be transfused with at least 8 units of PRBCs annually during the study
- Women of child-bearing potential using effective methods of contraception during dosing of study treatment (see 'Women of Child-bearing Potential' section below for details of acceptable contraceptive methods).

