- f. Visit 4.01: At Week 3, Serum Creatinine is drawn and Creatinine Clearance is calculated
- g. Captured in Source Documentation only
- 1. Hemoglobin/Transfusion History: collect retrospective data for the 6 months prior to study entry
- 2. Bone marrow for cytogenetics and morphology is not required if the exam has been completed within 6 months of the screening date and the patient has been hematologically stable. Patients with a major hematological response per IWG criteria (Post Text Supplement 4) may undergo an additional bone marrow biopsy or aspiration plus bone marrow examination at the time of response if in the opinion of the investigator the information may be helpful in the management of the patient. Bone marrow examination should also be performed if the patient is suspected to have had an AML progression.
- 3. Bone marrow aspirate should include cytogenetics and morphology
- 4. Repeat bone marrow aspiration and cytogenetics, iron stains and biopsy recommended at the time of hematological improvement per IWG criteria (Post Text

	Screening		Randomization	Treatment Period												Week 372 a End of Treatment	3-day F	Evaluation c Period	Study Evaluation Completion	Survival d Follow-Up			
Visit	1	2	3 e	4 f	5	6	7	8	9	10	11	12	13	14	15	16	17	18-96	777	501	502, 503, etc.	778	701, 702, etc.
Week 	-5 1	to -	Day 1	2	4	8	12	16	20	24	28	32	36	40	44	48	52	56 368	372				

Supplement 4). Bone marrow examination should also be performed if the patient is suspected to have experienced disease progression.

- 5. ECG and ECHO will be performed at screening and approximately every 3 months (Weeks 12, 24, 36, 52, 64, 76, 88, 104, 116, 128, 140, 156, 168,180,192,208 220, 232, 244, 260, 272, 284, 296, 312, 324, 336, 348, 364, 372). Patients in the Evaluation Period will have ECGs, ECHOs performed approximately every 3 months
- 6. Chest x-ray to be performed at baseline and for any hospitalization related to CHF (pulmonary edema)
- 7. Liver Ultrasound will be performed at Screening Visit 1 and anytime during the trial if liver function impairment or liver cirrhosis is suspected. Liver biopsy will be performed if abdominal ultrasound results indicated liver damage/failure and there are no contraindications, then liver biopsy is recommended

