# 7.1 Information to be collected on screening failures

A screening log of all patients screened for this study, at each study center, will be kept. This log will include patient number, demographic details, and reason why the patient was a screen failure. Sites should also maintain pre-screening logs capturing all of the reasons why a patient was not eligible for screening. The following information of patients who are screened but fail to be randomized will be collected in the eCRF: demographics, screening log and serious adverse events.

Should a patient screen fail but subsequently become eligible by newly meeting entry criteria resulting from a change in their parameters or due to a protocol amendment, patients may be re-screened. All screening labs outlined in Screening Visit 1 and Screening Visit 2 must be repeated. All other procedures (ECHO, abdominal ultrasound, bone marrow biopsy or aspiration, ocular and audiometery examinations, etc.) do not need to be repeated if they have been performed within 6 months of the original screening visit date.

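### Read literally, the SAP's per-protocol rule requires a bone marrow biopsy where the protocol requires only an examination, so patients who qualified by aspirate alone would be dropped from the PPS sensitivity analysis

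*SAP*

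**What the plan says.** SAP section 2.2.2 lists conditions that take a patient out of the PPS. After the conditions on first medication and underlying disease, a second list opens with "Also patients with the following protocol deviation will be excluded from the PPS". Its first item is "No bone marrow biopsy within 6 months of entering study".

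The protocol's entry requirement is worded differently. Section 5.1 says of the low or int-1 risk classification: "This must be confirmed by a bone marrow examination within 6 months prior to study entry and must be hematologically stable". It names no type of specimen. The Table 7-1 footnotes in section 7 bear on the same assessment:

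- Footnote 2: "Bone marrow for cytogenetics and morphology is not required if the exam has been completed within 6 months of the screening date".
- Footnote 3: "Bone marrow aspirate should include cytogenetics and morphology".

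For patients who are re-screened, section 7.1 lists procedures including "bone marrow biopsy or aspiration, ocular and audiometery examinations" and says that these "do not need to be repeated if they have been performed within 6 months of the original screening visit date".

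Protocol section 10.1 defines the PPS by correct first study medication and by absence of deviations from the inclusion criteria that concern the underlying disease. It gives examples and does not mention a biopsy. SAP section 4, which records departures from the protocol's analyses, lists only the redefinition of newly occurring neutropenia and thrombocytopenia.

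**The concern.** A biopsy is one kind of bone marrow examination, and an aspirate is another. A patient whose risk group was confirmed by aspirate within the window has met the inclusion criterion and has no deviation. The SAP item as written nevertheless counts that patient as deviating and excludes them.

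The PPS is the secondary analysis set for the primary endpoint, event-free survival. It is meant to show whether the FAS result holds among patients who met the disease criteria and received the assigned drug first. Removing eligible patients by specimen type serves neither purpose. It costs precision, and it makes any gap between the PPS and FAS results harder to explain. Because the change is not listed in SAP section 4, a reader of the study report would not know that the set had been narrowed.

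**Working it through.** The plan gives no figure to reproduce: the sample size of 210 rests on feasibility, and nothing is calculated for the PPS. The check is a comparison of texts, followed by an illustration of size under stated assumptions.

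**Step 1: specimen type**

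| Place | What satisfies it |
|---|---|
| Protocol 5.1 | An examination; specimen not named |
| Protocol Table 7-1, footnote 2 | A prior exam with cytogenetics and morphology |
| Protocol Table 7-1, footnote 3 | States what an aspirate should cover |
| Protocol 7.1 (re-screening) | Biopsy or aspiration |
| Protocol 7.5.9 (on-study) | Biopsy or aspiration |
| SAP 2.2.2 | Biopsy only |

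SAP 2.2.2 alone restricts the specimen. An aspirate-only patient passes every protocol row and fails the SAP row.

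**Step 2: is the narrowing declared?** Section 10.1 of the protocol can reasonably be read to cover failure of the marrow confirmation, since that confirmation is part of the MDS inclusion criterion. What it does not cover is the restriction to biopsy. SAP section 4 is silent on it.

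**Step 3: time anchor.** The SAP counts from entry to the study, and so does inclusion criterion 5.1. Footnote 2 counts from the screening date, and section 7.1 from the original screening visit. Protocol section 4 allows up to 35 days of screening. Take a marrow examination that is 5.5 months old at a visit 35 days before randomization. Using the SAP's month of 30.4375 days:

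35 / 30.4375 = 1.15 months; 5.5 + 1.15 = 6.65 months at randomization.

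That patient satisfies footnote 2. Whether they satisfy criterion 5.1 or the SAP item depends on whether study entry means screening or randomization, which neither document defines. The tension is therefore inside the protocol, and the SAP inherits it.

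**Step 4: size.** The documents do not report how many patients qualified by aspirate alone. Let s be that share (an assumption), with N = 210 planned:

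- removed = 210 × s
- retained = 210 × (1 − s)
- inflation of the standard error of the log hazard ratio ≈ 1/√(1 − s), if events fall in proportion to patients

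| s (assumed) | Removed | Retained | Standard error factor |
|---|---|---|---|
| 10% | 21 | 189 | 1.05 |
| 25% | 52.5, about 53 | about 157 | 1.15 |
| 50% | 105 | 105 | 1.41 |

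These are counts before any other PPS exclusion. With s = 0 nothing changes. The FAS is unaffected at every s.

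**The case against.** The strongest reply is that biopsy here is shorthand. The item stands under a heading about protocol deviations, and a patient qualified by aspirate has none. The SAP is loose with the term elsewhere: for AML confirmation it says biopsy in section 2.5.1, aspirate in 2.5.3.5, and biopsy or aspirate in Table 1-1 and 2.7.1.4. PPS exclusions also follow a separate document (VAP M3) that is not available here and may already code the item as an examination. This stands: actual removal of compliant patients is not shown. It does not excuse the wording, because the SAP names both specimens where it means both, so a programmer could reasonably take this line at its word.

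It is also fair to say that the consequence is small. The PPS supports one of several sensitivity analyses of an endpoint that is tested only in an exploratory sense. The type of marrow specimen is fixed before randomization, so the exclusion should not differ systematically between arms. The expected cost is in precision and generalizability, not a biased comparison.

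A reader might also infer that the SAP uses the wrong time anchor. The documents do not support that: the inclusion criterion itself counts from study entry, as the SAP does.

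**Conclusion.** The mismatch is real and lies in the current text of both documents. Applied literally, SAP section 2.2.2 drops from the PPS patients who met the inclusion criterion by aspirate alone, and the SAP does not declare this. The conclusion rests on one condition, literal application of the item. Its numerical effect depends on the aspirate-only share, which is unknown. Only the PPS analysis of event-free survival is touched.

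Three stronger readings go beyond the documents. One is that the PPS could no longer serve as a check on the FAS result; at most it is weakened to an unknown degree. Another is that it would over-represent centers that routinely take biopsies; nothing in the documents describes biopsy practice by center. The third is that the protocol's PPS definition leaves no room for any marrow condition; marrow confirmation belongs to a disease-related inclusion criterion, and only the restriction to biopsy is new.

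**What to change.** 1. Replace the item in SAP section 2.2.2 with: *No bone marrow examination (biopsy or aspirate) within 6 months prior to study entry*.
2. Apply the same wording in the deviation code, and in VAP M3 if it carries the item, before unblinding.
3. Reconcile study entry in protocol section 5.1 with the screening date in Table 7-1 footnote 2 and section 7.1. Then state one anchor in the SAP, so that a patient who complied with the visit schedule is not excluded on timing.
4. If a biopsy-only rule is intended after all, declare it in SAP section 4 with a reason, and report how many patients it removes from each arm.

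The cost is one line of SAP text, one definition of the time anchor and a check of the deviation code. No new data are needed, and the primary analysis does not change.
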